2.6.6 Treatment

Protocol treatment status as of the clinical data cut-off will be summarized. In this report, status will be summarized by treatment assignment. Time from randomization to treatment termination will be summarized using KM curves according to treatment assignment.

Per SOLE Data Manager’s Hand Book v3.0 (dated 21Mar13), for Arm B patients, interruptions should be every 9 months and should last for 3 months in years 1-4. Any interruption up to 4 months is considered a “protocol-specified interruption” and the reason for interruption is defined as “protocol-defined interval” on L forms; any interruption of 4 months +1 day (121 days or more) is considered a “non-protocol interruption”.

The Idealized Scheduler contains a link to an Excel file on the IBCSG web site. This file calculates the letrozole dispensation and interruptions (Arm B) based off of the Randomization Date.

Treatment variation scenarios:

- Patient on Arm B stops letrozole early (e.g., at Month 6 instead of Month 9). The patient should stop for three months. Patient should re-start letrozole and continue until the pre-defined date of the next interruption. This will get the patient back on schedule.
- Patient on Arm B took medication during the protocol-specified interruption. Patient should continue until Month 9 of the next year and then start the interruption. This will get the patient back on schedule.
- Patient forgot to take some pills and therefore has some left at the date the interruption should start. The patient should not finish the medication. The patient should interrupt on the pre-defined date to stay on schedule.

For Arm A patients, not-per-protocol interruptions are those of over a month in duration.

Reasons for treatment interruptions will be summarized by treatment assignment. Note that there could be more than one reason for an interruption spanning more than one L Form: for example, a patient start interruption per protocol on one L form, but due to adverse event, the interruption continues to the next L form without restarting after 4 months. The first reason would be “protocol-defined interval” and then the second reason would be “Adverse Event”.

Based on information on Data Manager’s Handbook, to describe adherence with protocol-assigned treatment, the following tables and figures are proposed.

Table 2.6.6.1. Patients’ Treatment Compliance by treatment assignment

	Arm A		Arm B		Overall	
	N	%	N	%	N	%
Did not start protocol treatment						
Receiving protocol treatment						
Stopped all study treatment						
Completed treatment per protocol						
Stopped all study treatment early						

Adverse event						
Disease related						
Patient decision						
Other						
Patient Lost to Follow-up						
Treatment status unknown due to missing information on forms						
Total number of patients w. treatment data available						

Table 2.6.6.2. Days of Treatment on by treatment assignment during year one to five

Year	Arm A			Arm B		
	N	Median	IQR	N	Median	IQR
1						
2						
3						
4						
5						

Note: N is total number of patients on treatment during that treatment year

Table 2.6.6.3 Number of patients with per-protocol interruptions and resumes for patients on Arm B only

Year	Per-protocol Interruption			Per-protocol Resume		
	n	N	% (n/N)	n	N	% (n/N)
1						
2						
3						
4						
Overall						

Note: N is total number of patients on treatment any time during the treatment year

Table 2.6.6.4 Not-per-protocol interruptions for patients on Arm A and Arm B

Year	Arm A			Arm B		
	n	N	%	n	N	%
1						
2						
3						
4						
5						

Note: N is total number of patients on treatment any time during the treatment year

Table 2.6.6.5 Reasons for treatment interruptions by treatment assignment

Reasons	Arm A		Arm B	
	N	%	N	%
Protocol-defined interval (Arm B only)				
Patient decision				
Medical decision				
adverse event				
Other				

Note: there could be more than one reason for an interruption spanning more than one L Form

Figure 2.6.6.1 Percentage of patients on treatment by month, according to treatment group (x-axis: month 1 to 60, y-axis: percentage)

Figure 2.6.6.2 Percentage of patients on treatment by 3-month intervals, according to treatment group (x-axis: interval 1 to 20, y-axis: percentage)

Figure 2.6.6.3 Mean percentage of days on treatment during 3-month intervals, according to treatment group (x-axis: interval 1 to 20, y-axis: mean percentage)

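### SAP 2.6.6 does not confine Arm B's 121-day interruption threshold to the scheduled breaks, so an unscheduled stop of 31 to 120 days counts in Arm A but not in Arm B of Table 2.6.6.4

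*SAP*

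**What the plan says.** SAP 2.6.6 first describes the Arm B schedule: "for Arm B patients, interruptions should be every 9 months and should last for 3 months in years 1-4". The classification rule follows, citing the Data Manager's Hand Book: "Any interruption up to 4 months is considered a “protocol-specified interruption” and the reason for interruption is defined as “protocol-defined interval” on L forms". The other side of the cut is: "any interruption of 4 months +1 day (121 days or more) is considered a “non-protocol interruption". Arm A has its own rule: "For Arm A patients, not-per-protocol interruptions are those of over a month in duration".

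Two table shells depend on these definitions. Table 2.6.6.4, titled "Not-per-protocol interruptions for patients on Arm A and Arm B", has a row for each of years 1 to 5 and columns for both arms. Table 2.6.6.5 gives reasons for interruption by arm, with one row for the protocol-defined interval that applies to Arm B only. Table 2.6.6.3, which counts per-protocol interruptions in Arm B, has rows for years 1 to 4 and an overall row.

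The regimen is in Protocol 5.1 and SAP 1.2. Arm B has a three-month break at the end of each of years 1 to 4 and takes letrozole throughout year 5. Arm A takes it throughout all five years.

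**The concern.** The Arm B rule depends only on how long the stop lasts. It sets no start window, makes no link to the Scheduler date and has no year limit. A woman in Arm B who stops for 60 days at an unplanned time therefore falls under the same allowance as one taking her scheduled break, while a woman in Arm A with the same 60-day stop is counted as not per protocol.

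Table 2.6.6.4 exists to compare such stops between arms. If the two arms behaved identically outside the scheduled breaks, the table could still show fewer unplanned interruptions in Arm B, purely because of the definition. On the literal reading Table 2.6.6.5 is affected too: an Arm B stop of up to 120 days made because of an adverse event would be filed under the protocol-defined interval, while the same stop in Arm A would appear under adverse event. The schedule of interruptions is the experimental treatment here, so readers will look at these tables.

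**Working it through.** **Inputs.** Arm B threshold: 121 days or more, described as four months plus one day (SAP 2.6.6). Arm A threshold: over a month (SAP 2.6.6). Scheduled Arm B break: 3 months, years 1 to 4 only (SAP 2.6.6, SAP 1.2, Protocol 5.1).

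**Step 1: the SAP's month.** (121 − 1) / 4 = 30 days. The SAP's own figure is consistent with 30-day months. On that convention Arm A's rule starts at 31 days. The SAP does not give the Arm A limit in days, so the 31 is inferred.

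**Step 2: scheduled breaks.** Arm B: 120 − 3 × 30 = 30 days of grace beyond the planned break. Arm A: 30 − 0 = 30 days of grace. For scheduled breaks the arms are treated alike.

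**Step 3: unscheduled stops, rules applied as written.**

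| Length of stop (days) | Counted in Arm A | Counted in Arm B |
|---|---|---|
| 20 | no | no |
| 31 | yes | no |
| 60 | yes | no |
| 90 | yes | no |
| 120 | yes | no |
| 121 | yes | yes |

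The rules disagree for every length from 31 to 120 days, which is 120 − 31 + 1 = 90 day-lengths.

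**Step 4: year 5.** Neither arm has a planned break, so the Arm B allowance has nothing to allow for. A single stop can last 120 / 365.25 = 33% of the year in Arm B without being counted, against 30 / 365.25 = 8% in Arm A.

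**Step 5: the narrower reading.** Suppose the sentence on the year 1 to 4 schedule limits the rule that follows it. The four-month allowance then covers scheduled breaks only, and the SAP states no threshold for an Arm B stop of 31 to 120 days outside them. Table 2.6.6.4 still has Arm B cells to fill for all five years.

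**Step 6: does other SAP text settle it?** The worked example starts from the case where "a patient start interruption per protocol on one L form" and then runs over, so it concerns a scheduled break. The first variation scenario ("Patient on Arm B stops letrozole early (e.g., at Month 6 instead of Month 9") and the two after it say how to bring a patient back on schedule, not how to classify the stop. The protocol gives the regimen and pill counts and does not classify interruptions.

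**The case against.** The strongest reply is that the literal reading is not what the authors meant. The rule comes straight after the description of the year 1 to 4 schedule, and its label is that of a protocol-defined interval. Table 2.6.6.3 has no year-5 row, whereas Table 2.6.6.4 has one for Arm B. A reader might infer from the literal rule that the SAP excuses Arm B stops in year 5 as per protocol. The documents do not support that: the shells suggest year-5 stops are not meant to be per protocol. This stands, but it supplies no threshold. The only Arm B cut-off stated anywhere is 121 days.

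A second reply is that the Data Manager's Hand Book may define this more closely. It may. It is not among the documents, and the SAP text that defines the tables carries no such limit.

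A third is that little depends on it. That also stands. Table 2.6.6.2 and Figures 2.6.6.1 to 2.6.6.3 show time on treatment without any threshold, Table 2.6.6.1 gives reasons for stopping early, and adverse events are analysed separately in SAP 2.6.5.

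Two further inferences should be resisted. The unequal thresholds are not unfair in themselves, since Step 2 shows equal grace for scheduled breaks. Nor is Table 2.6.6.4 the only between-arm view of unplanned interruptions, because Table 2.6.6.5 also counts interruptions by arm for patient decision, medical decision, adverse event and other reasons.

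**Conclusion.** The point holds as a minor defect. As written, SAP 2.6.6 counts an unscheduled stop of 31 to 120 days in Arm A and not in Arm B. Read in context, it leaves Arm B without a threshold for such stops. Either way the Arm B column of Table 2.6.6.4 is not defined comparably with Arm A, most plainly in year 5. Table 2.6.6.5 is affected only on the literal reading.

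The 31-day lower limit rests on the SAP's implied 30-day month. How many women would be misclassified cannot be estimated, because the documents give no frequencies or durations of unscheduled stops. A reader might infer that the comparison of efficacy or tolerability is biased. It is not: the ITT analysis of DFS, alpha and the 647 events do not use this classification, and neither do the adverse event analyses.

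**What to change.** Add to SAP 2.6.6, before database lock:

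> The 4-month limit applies only to the scheduled Arm B break in years 1-4 (including an early break taken in its place under the first variation scenario). Any other Arm B interruption, including any in year 5, is not-per-protocol if it lasts over a month, as in Arm A, and is tabulated under its recorded reason.

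If the Hand Book sets a window for when a scheduled break may start, that window applies. The change needs no new data. It uses the on and off dates that Table 2.6.6.2 and the figures already require, and the Scheduler dates, of which the SAP says "This file calculates the letrozole dispensation and interruptions (Arm B) based off of the Randomization Date".

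The costs are slightly more programming and Arm B not-per-protocol percentages that may rise. For stops already coded as the protocol-defined interval, the true reason may be unrecoverable, so Table 2.6.6.5 may be only partly repaired. Some judgement also remains over how early a break can begin and still count as the scheduled one, unless the Hand Book settles it.

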1.2 TRIAL DESIGN

SOLE (IBCSG 35-07 / BIG 1-07) OVERVIEW

Title:	Study Of Letrozole Extension (SOLE): A phase III trial evaluating the role of continuous letrozole versus intermittent letrozole following 4 to 6 years of prior adjuvant endocrine therapy for postmenopausal women with hormone receptor positive, node-positive early stage breast cancer.
Patient Population:	Postmenopausal women who are disease-free following 4-6 years of prior adjuvant endocrine therapy with selective estrogen receptor modulator(s) (SERM) and/or aromatase inhibitor(s) (AI) for endocrine-responsive, node-positive early breast cancer.
Entry:	Patients must have stopped prior endocrine SERM/AI therapy, and must be randomized within 12 months (1 year) of the last dose of prior endocrine SERM/AI therapy.
Activation Date:	8 November 2007 (First patient randomized on 5 December 2007)
Target Accrual:	4800 patients
Closure Date:	12 July 2012 (Last patient randomized on 8 October 2012)
Final Accrual:	4884 patients

Trial Schema:

The SOLE trial is a multinational phase III randomized clinical trial designed to compare continuous letrozole for 5 years with intermittent letrozole over a 5-year period among postmenopausal women who are disease-free following 4 to 6 years of prior adjuvant endocrine therapy with SERM(s) and/or AI(s) for endocrine-responsive node-positive operable breast cancer. The hypothesis is that introducing 3 month treatment-free intervals during the course of 5 years of extended letrozole will improve disease-free survival.

The randomization was stratified according to participating center and prior SERM/AI endocrine therapy (SERM(s) alone, AI(s) alone, both SERM(s) and AI(s)). Patients were randomized 1:1 to one of two extended adjuvant endocrine therapy groups:

A: Continuous letrozole 2.5 mg daily for 5 years

B: Intermittent letrozole 2.5 mg daily for the first 9 months of years 1 through 4, with treatment-free intervals for the last 3 months of years 1 through 4, followed by 12 months of letrozole 2.5 mg daily in year 5

Patients should start trial treatment as soon as possible after randomization. Trial treatment should begin no later than 6 weeks from the date of randomization. All patients will be followed every 6 months for years 1 to 5, and yearly thereafter for assessment of disease status and for survival data collection.

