2.4 FOLLOW-UP

Number of DFS events per person-year of follow-up is calculated at each DSMC review time to guide the timing for the database lock. The data cut-off is planned for prior to November 1, 2016 when we expect the number of DFS events will reach the target of 647 for the analysis with database lock in Q1 2017. Data as of the database cut-off will be used for analysis.

Median follow-up is calculated from the Kaplan-Meier estimate of overall survival, with the event/censoring indicator inverted (i.e. alive as event and dead as censored).

Updated results will be presented every two to three years thereafter.

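### Year-5 rows of Tables 2.6.6.2 and 2.6.6.4 count patients whose fifth year is cut short by the data cut-off, so the year-5 interruption percentage is somewhat too low

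*SAP*

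**What the plan says.** SAP 2.6.6 proposes tables to describe adherence. Table 2.6.6.2 gives N, median and IQR of days on treatment for years 1 to 5, by arm, with the footnote "Note: N is total number of patients on treatment during that treatment year". Table 2.6.6.4 gives the number and percentage of patients with not-per-protocol interruptions for the same years; its N is likewise everyone on treatment at any time in the year. For Arm A such an interruption lasts more than a month; for Arm B it lasts 121 days or more.

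The calendar is in two other sections. SAP 1.2 records "First patient randomized on 5 December 2007", accrual closure on 12 July 2012, "Last patient randomized on 8 October 2012" and a final accrual of "4884 patients". SAP 2.4 says "The data cut-off is planned for prior to November 1, 2016 when we expect the number of DFS events will reach the target of 647", and then "Data as of the database cut-off will be used for analysis".

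SAP 2.6.6 does not restrict a row to completed treatment years, scale days to the time available, or say how to treat a patient who reaches the cut-off in mid-year.

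**The concern.** A patient randomized on the last accrual day has about 24 days of year 5 before 1 November 2016. She is on treatment during that year, so she belongs in N for both tables. She can contribute at most those days to Table 2.6.6.2, and she has almost no chance of showing a long interruption in Table 2.6.6.4. Years 1 to 4 are essentially complete, because the last patient reaches four years on 8 October 2016. The problem is therefore confined to year 5.

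Year 5 is the only year in which both arms are scheduled for 12 months of drug, so it is where a reader looks to see whether Arm B returned to full treatment. An interruption percentage whose denominator includes unobserved time looks better than it should, and it is not comparable with years 1 to 4.

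**Working it through.** The plan gives no figure for the share of patients completing year 5 by the cut-off, so there is none to reproduce. The only design number involved is the 647 events that set the cut-off, and it checks. Schoenfeld's formula at HR 0.80 gives 631 and Freedman's 636; with O'Brien-Fleming inflation of 1.020 they become 643 and 648.

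**1. Share truncated in year 5.** Inputs are the SAP 1.2 dates and a cut-off of 1 November 2016, the latest date that SAP 2.4 allows. Patients randomized after 1 November 2011 have under five years.
- Uniform accrual to the last randomization: 342 / 1769 days = 19.3%, about 944 of 4884. Observable year-5 time runs from 24 to 365 days, mean 194.5.
- Uniform accrual with almost none after the 12 July 2012 closure: 254 / 1681 = 15.1%, about 738. Observable time runs from 112 to 365 days, mean 238.5.
- Late accrual (last 342 days) at half the earlier rate: 171 / (1427 + 171) = 10.7%. At double the rate: 684 / (1427 + 684) = 32.4%.
- Earlier cut-off, uniform accrual: 21.1% at 1 October 2016, 22.8% at 1 September 2016.

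These are shares of randomized patients. They carry over to the year-5 N if leaving treatment before year 5 is unrelated to entry date.

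**2. Table 2.6.6.4.** Let f be the truncated share, with observable time O uniform over the ranges above. Suppose interruptions of length L start uniformly and must reach length L within the year to be classified. The relative shortfall is then f × [1 − E max(O − L, 0) / (365 − L)].
- f = 19.3%, L = 31: E = 334² / (2 × 341) = 163.6; 0.193 × (1 − 163.6/334) = 9.9%.
- f = 19.3%, L = 121: E = 244² / (2 × 341) = 87.3; 0.193 × (1 − 87.3/244) = 12.4%.
- f = 15.1%, L = 31: E = 238.5 − 31 = 207.5; 0.151 × (1 − 207.5/334) = 5.7%.
- f = 15.1%, L = 121: E = 244² / (2 × 253) = 117.7; 0.151 × (1 − 117.7/244) = 7.8%.

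Two other counting conventions widen this to roughly 5% to 15%. If an interruption counts as soon as it starts, the 15.1% case gives 0.151 × (1 − 238.5/365) = 5.2%. If starts are spread over all 365 days and completed years miss none, the 19.3% case with L = 121 gives 0.193 × (1 − 87.3/365) = 14.7%. At the extreme 32.4% share, the main formula gives about 17% (L = 31) to 21% (L = 121).

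**3. Table 2.6.6.2.** Let p be the proportion stopping early within year 5, independent of entry date. A full 365 days is recorded for (1 − f)(1 − p) of patients.
- Lower quartile below 365 requires (1 − f)(1 − p) < 0.75, so p > 1 − 0.75/(1 − f): 7.0% at f = 19.3%, 11.7% at f = 15.1%. If f exceeds 25%, no early stopping is needed.
- Median below 365 requires p > 1 − 0.50/(1 − f): 38% and 41%.
- With stopping times uniform over the year, the lower quartile at f = 19.3% is about 333 days for p = 10%, 288 for 15% and 253 for 20%. At f = 15.1% it is still 365 for p = 10% and about 333 for 15%. Without truncation it would be 365 in all of these cases.

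The documents give no year-5 stopping rate, so each p is an assumption.

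**The case against.** The strongest reply is that little in these outputs is actually wrong. Table 2.6.6.2 reports only N, median and IQR. At 15% to 19% truncation with full adherence, the median and both quartiles stay at 365 days. A reader might infer that the table displays the cut-off as lost exposure, pointing to a year-5 mean that falls from 365 to about 332 days under full adherence and f = 19.3%. The documents do not support that reading: the table reports no mean, and its lower quartile moves only with early stopping or an accrual shape that must be assumed. This part of the objection stands.

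It is also fair that the tables are descriptive, that concurrent 1:1 randomization should make truncation about equal in the two arms, and that women who stopped, relapsed or died before year 5 are not in N.

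Other outputs help only in part. Table 2.6.6.1 has a row for patients still receiving treatment, and time to treatment termination is shown by Kaplan-Meier curves. Neither gives days per year or interruptions, so neither corrects the year-5 rows. Figure 2.6.6.3 plans a mean percentage of days on treatment by 3-month interval, but does not state its denominator. The shortfall in Table 2.6.6.4 needs no threshold and remains.

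**Conclusion.** The point holds as a minor, inexpensive improvement. The stated denominators make the year-5 interruption percentage in Table 2.6.6.4 too low, by roughly 5% to 15% in relative terms. This assumes uniform accrual, interruption starts spread evenly over the year, and a cut-off at the latest permitted date. The documents give no accrual curve, so the truncated share could be about 11% to 32%, and an earlier cut-off raises it. In Table 2.6.6.2 the median is safe; only the lower quartile is at risk, under the conditions shown above.

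A reader might also infer a bias between arms or a threat to the trial's conclusion. Neither follows. Truncation should be balanced, although the shortfall in Table 2.6.6.4 can differ by a few percent in relative terms because the arms use different duration limits. The DFS comparison does not use these tables.

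**What to change.** In Tables 2.6.6.2 and 2.6.6.4, limit each year's N to patients whose treatment year, counted from randomization, ended on or before the data cut-off. Keep in N those who were on treatment in that year and stopped early within it, since they are the non-adherence the tables should show. Add a footnote with the number still inside year 5 at the cut-off, by arm.

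If days are instead shown as a percentage of observable days, observable time should end at the data cut-off, death or loss to follow-up. It should not end at stopping of treatment, which would remove early stopping from the result.

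The cost is one line of SAP text and one filter in the table program. The downside is a smaller year-5 N: about 81% to 85% retained under uniform accrual (roughly 3,940 to 4,146 of 4884, before removing those who left treatment earlier).
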